Include the version number and date of this protocol.

Response: 1

REVISION HISTORY

| Revision # | Version Date | Summary of Changes | Consent Change? |
|-------------------|---------------------|------------------------------|------------------------|
| 1 | 10/7/2021 | Pre/post evaluation measures | No |
| | | | |
| | | | |
| | | | |
| | | | |

FUNDING:

Indicate any funding for this proposal. This should match the Funding Sources page in Click IRB.

Response: 2019-20 SUNY Research Seed Grant Program RFP #20-02-RSG

GRANT APPLICABILITY:

Indicate whether this protocol is funded by a grant (e.g. NIH, foundation grant). For a grant with multiple aims, indicate which aims are covered by this research proposal.

NOTE: This question does not apply to studies funded by a sponsor contract.

 *Include a copy of the grant proposal with your submission.*

Response: 2019-20 SUNY Research Seed Grant Program RFP #20-02-RSG Aim 2 Investigate the potential of reinforcing the retention of cable-actuated training by providing auditory feedback to eight adults with cerebral palsy

RESEARCH REPOSITORY:

Indicate where the research files will be kept, including when the study has been closed. The repository should include, at minimum, copies of IRB correspondence (approval, determination letters) as well as signed consent documents. This documentation should be maintained for 3 years after the study has been closed.

Response: The copies of IRB correspondence or signed consent forms will be stored in a locked cabinet located in Furnas Hall Room 809. Only personnel related to the project will have access to the document.

Location: Cabinet with key access

Address: [name]

Department: Dept of Mechanical and Aerospace Engineering

1.0 Study Summary

| | |
|---|--|
| Study Title | Novel Gait Training Paradigm to Promote Healthy Aging in Individuals with Cerebral Palsy |
| Study Design | Adults with cerebral palsy will be recruited to conduct the feasibility testing of our hypothesis for multiple training sessions. |
| Primary Objective | The purpose of this study is to create a platform to prolong the adaption obtained from the cable-actuated gait training and encourage the individuals with CP to provide self-care at home. |
| Secondary Objective(s) | Investigate the potential of reinforcing the retention of cable-actuated training by providing auditory feedback to adults with cerebral palsy |
| Research Intervention(s)/ Investigational Agent(s) | This study includes cable-actuated strength training and auditory feedback to reinforce the feedback. |
| IND/IDE # | N/A |
| Study Population | Adults with Cerebral Palsy |
| Sample Size | 20 |

| | |
|---|---|
| Study Duration for individual participants | 2 Years |
| Study Specific Abbreviations/ Definitions | sEMG: surface electromyography DOF: degree of freedom CP : cerebral palsy |

2.0 Objectives*

2.1 Describe the purpose, specific aims, or objectives of this research.

Response: (1) Investigate the benefit of the strength training of adults with cerebral palsy using a cable-actuated robot.
 (2) Investigate the potential of reinforcing the retention of cable-actuated training by providing auditory feedback to eight adults with cerebral palsy.

2.2 State the hypotheses to be tested, if applicable.

NOTE: A hypothesis is a specific, testable prediction about what you expect to happen in your study that corresponds with your above listed objectives.

Response:

- (1) We hypothesized that individuals with cerebral palsy will benefit from the cable-actuated strength training to improve their walking ability and posture.
- (2) We hypothesized that auditory feedback will reinforce the retention of cable-actuated training.

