5.0 Study Design*

5.1 *Describe and explain the study design (e.g. case-control, cross-sectional, ethnographic, experimental, interventional, longitudinal, observational).*

Response: The experiment protocol involves a maximum of ten sessions and will take two or three hours for each session. Baseline data will be collected before the first session for both overground and treadmill walking. During this session, the sound level will be adjusted based on the feedback received from the users. The researcher will ask the comfortable sound level to the participant before starting the experiment. Training will be conducted on the treadmill with the cable-actuated device for about 20 minutes. When the cables were removed, participants walked on the treadmill for 4 minutes during the post-training session. During training and post-training, participants will be exposed to feedback while walking on the treadmill. After treadmill walking, CP participants will be asked to take a ten-minute break and then practice overground walking for two minutes with auditory feedback (type A) and without it (type B). Effects of 3 different types of

auditory feedback will be explored namely, rhythmic sounds, movement sonification, and sound notifying erroneous gait. Group A participants will be further divided into groups depending on the type of auditory feedback that will be provided. Participants will participate in a maximum of 10 sessions, two or three times a week. Before the first and after the last training, participants will be evaluated for functional gait assessment, 6-min-walk, leg strength using a dynamometer, international physical activity questionnaire (short form), usability questionnaire, and Modified Ashworth test by a physical therapist.

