of training with a cable-actuated robot will be provided. The device will augment 15% of their own body weight. While they are walking with the device, auditory feedback will be provided for the participants who are assigned to the auditory group. The auditory and non-auditory groups will be randomly assigned. Furthermore, one of the 3 different types of auditory feedback will be randomly assigned to participants from the feedback group. A break of 5 minutes will be provided after 10 minutes of walking with the device. After the robotic training is completed, the device will be taken off and the participant will walk without the device to monitor the immediate retention of the training. After every 10 minutes, the researcher will ask the participant questions as per the Borg exertion scale to check the fatigue of the participant. After finishing the treadmill session, participants will take a 10-minute break and walk 4 minutes with (or without auditory feedback) on the floor. The participant will repeat overground walking for a total of three sets. There will be a total of ten training sessions, two or three sessions a week and each session will last for a maximum of 3 hours. In addition, pre and post-training visits are required to evaluate functional gait assessment, 6-min-walk, leg strength using a dynamometer, international physical activity questionnaire (short form), usability questionnaire, and Modified Ashworth test by a physical therapist.

12.2 Describe what data will be collected.

NOTE: For studies with multiple data collection points or long-term follow up, consider the addition of a schedule or table in your response.

Response:

- We will schedule the participants to visit the lab. We will make a table when the participants are available.
- *EMG data from the muscles*
- *Vicon motion capture data*
- *Photo and Video of the test*
- *IMU sensor data*
- *Smart insole data*
- *Ground reaction force*

12.3 List any instruments or measurement tools used to collect data (e.g. questionnaire, interview guide, validated instrument, data collection form).

Include copies of these documents with your submission.

Response: Vicon motion capture system, Delsys Trigno sEMG system, and Bertec Force plate instrumented treadmill, Smart Insole

12.4 Describe any source records that will be used to collect data about subjects (e.g. school records, electronic medical records).

Response: N/A

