NOTE: This may not apply to certain types of studies, including chart/records reviews, survey studies, or observational studies. This question is asked to elicit whether the investigator has an adequate sample size to achieve the study objectives and justify a conclusion.

Response: A goal of this study is to test the feasibility and efficacy of the proposed intervention in the improvement of gait characteristics. Currently, no previous study is available to have the treatments both resistance training and sensory feedback. For CP subjects, we will have a sample size of 20 (10 each group), which requires an effect size of 0.5 to have a power of 80% with the size of the test 0.05 in the two-group comparison with 6 repeated measures under the assumption of compound symmetry with auto-correlation 0.1.

19.3 Describe any procedures that will be used for quality control of collected data.

Response: The post-processed data will be visually investigated whether all the procedures were properly applied. Outliers will be also detected during this investigation.

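### Hypothesis 1 claims benefit from cable training, but every participant receives it, so the design can show only uncontrolled within-participant change

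*Combined protocol and SAP*

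**What the plan says.** Objective 1 in Section 2.1 reads "Investigate the benefit of the strength training of adults with cerebral palsy using a cable-actuated robot". Hypothesis 1 in Section 2.2 turns this into a prediction: "individuals with cerebral palsy will benefit from the cable-actuated strength training to improve their walking ability and posture".

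The training is described without any restriction by group. Section 5.1 says "Training will be conducted on the treadmill with the cable-actuated device for about 20 minutes", and Section 12.1 describes 20 minutes "of training with a cable-actuated robot will be provided". What is randomised is stated in Section 12.1: "The auditory and non-auditory groups will be randomly assigned", and "auditory feedback will be provided for the participants who are assigned to the auditory group". A second randomisation, to one of three feedback types, takes place inside the auditory group only.

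Section 3.0 names lower-body motion and muscle activation during walking as the two primary outcomes, and adds clinical tests before the first and after the last training. Section 19.1 takes change from baseline to end of treatment as the main statistic. Its mixed model has factors for time within day, day, feedback and random assignment. Section 19.2 opens with "A goal of this study is to test the feasibility and efficacy of the proposed intervention" and then gives power for the comparison of two groups of 10.

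On purpose, Section 1.0 speaks of feasibility testing and Section 19.1 calls the study a pilot on viability. The Primary Objective in Section 1.0 has two parts: to prolong the adaptation from the training, and to "encourage the individuals with CP to provide self-care at home".

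**The concern.** A statement that participants benefit from a treatment needs some view of what would have happened without it. Here nobody goes without it. If scores improve, the improvement may come from the cable device, from doing the tests a second time, from getting used to the treadmill, from up to ten sessions of walking, or from regression to the mean. In the auditory half of the sample it may also come from the feedback.

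At stake is the sentence that the trial report will carry. With the hypothesis worded as it is, a clear change from baseline to end of treatment would confirm it on paper and could be carried as device benefit into the larger trials that Section 19.1 has in mind. Nothing in the plan tells the analyst or the reader to stop short of that.

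There is a smaller mismatch of the same kind. The home self-care clause of the Primary Objective has no home procedure and no direct outcome behind it.

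**Working it through.** **Which contrasts exist for each hypothesis**

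- Hypothesis 2 (feedback): auditory versus non-auditory group, randomised, 10 against 10. This is a controlled comparison.
- Hypothesis 1 (cable training): no untrained, sham, treadmill-only, waiting-list or external control appears in Sections 5.1, 12.1 or 19.1, and there is no run-in with repeated baselines. The model in Section 19.1 has no trained-versus-untrained factor. Two contrasts remain, both within participants: (a) baseline to end of treatment, and (b) before versus after cable removal within a session.

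Contrast (a) is open to every rival explanation listed above. Contrast (b) spans a single session, so retesting after weeks plays no part in it, but it too has no condition without cables. The overground walking with and without feedback in Section 5.1 does not help, because those participants have all trained with the device.

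**The plan's own figure**

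There is none for Hypothesis 1. The 80% power in Section 19.2 concerns the feedback comparison and cannot be used to check this point. It does not reproduce from its stated inputs. With six measures and correlation 0.1, the SD of a participant's mean is √((1 + 5 × 0.1)/6) = 0.50, and an effect of 0.5 with 10 per group gives about 61% two-sided (normal approximation; 56% by t). That is a separate matter.

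**How often an ineffective device could appear to work (illustration)**

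Inputs:

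- n = 20, from Section 19.2.
- Two-sided level 0.05. Section 19.2 gives 0.05 without the sidedness; two-sided is assumed.
- True device effect zero, by construction.
- Retest shift of 0.1, 0.2 or 0.3 SD. Assumed; the documents give no figure.
- Pre/post correlation r of 0.1, 0.5 or 0.8. The value 0.1 is the within-participant correlation in Section 19.2; the other two are assumed.
- Paired t-test, used for simplicity. The plan specifies a mixed model.

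Formulas: SD of the change = √(2(1 − r)); noncentrality = shift/√(2(1 − r)) × √20; improvement is declared when t on 19 degrees of freedom exceeds 2.093.

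SD of the change: √1.8 = 1.342 at r = 0.1; √1.0 = 1.000 at r = 0.5; √0.4 = 0.632 at r = 0.8.

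For a shift of 0.3 the noncentralities are 0.3/1.342 × 4.472 = 1.00, 0.3/1.000 × 4.472 = 1.34 and 0.3/0.632 × 4.472 = 2.12.

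Probability of declaring improvement:

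| Retest shift | r = 0.1 | r = 0.5 | r = 0.8 |
|---|---|---|---|
| 0 | 2.5% | 2.5% | 2.5% |
| 0.1 SD | 5% | 6% | 10% |
| 0.2 SD | 9% | 13% | 27% |
| 0.3 SD | 16% | 25% | 52% |

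The right comparator is 2.5%, because a false claim of benefit needs the favourable direction.

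**The Primary Objective**

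Section 12.1 places all visits in the laboratory and schedules no home use of the insoles or the feedback, although the background in Section 4.1 looks ahead to unsupervised settings. Section 3.0 lists a physical activity questionnaire and a usability questionnaire. Neither is put forward as a measure of self-care at home. The part on prolonging adaptation is addressed by post-training and overground walking with and without feedback.

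**The case against.** The strongest reply is that this is a pilot and says so. Section 1.0 speaks of feasibility testing, and Section 19.1 says the purpose is to see viability and support later trials. That is true, and a before-after estimate is a reasonable thing for a pilot to produce. But the sentence in Section 19.1 is there to justify leaving family-wise error uncontrolled. It does not mention Hypothesis 1 and does not restrict what may be said about it.

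A reader might infer from Section 19.2 that the plan labels the before-after change as efficacy. The text does not go that far. It speaks of efficacy of the proposed intervention as a whole, and its power statement covers only the comparison of the two randomised groups. What remains is an ambiguity: the section does not say that only the feedback contrast can carry an efficacy statement.

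A reader might also infer that the Primary Objective cannot be answered at all. That is too strong. Only the home self-care clause lacks a procedure and a direct outcome.

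Two further replies stand in part. Retest learning is easiest to argue for the 6-minute walk and the functional gait assessment, which are not the primary outcomes; it need not carry over to kinematics or sEMG, although treadmill familiarity can. And the rates in the table rest on assumed shifts and a simpler test than the planned model, so they are not this plan's error rate. At the only correlation that the documents give, they are at the low end. The design argument does not depend on them.

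**Conclusion.** The point holds as one about wording and inference. As designed, the trial can estimate how much participants change while receiving cable training. It cannot attribute that change to the device, and nothing in the plan says so for Objective 1 or Hypothesis 1. The randomised feedback comparison is unaffected.

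The size depends on how large the non-device change is, which the documents do not tell us. Over assumed shifts of 0.1 to 0.3 SD and correlations of 0.1 to 0.8, a paired test in 20 people would declare improvement from an ineffective device between about 5% and 52% of the time.

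The mismatch over home self-care is secondary and confined to that clause.

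**What to change.** 1. Restate Objective 1 and Hypothesis 1 (Sections 2.1 and 2.2) as estimation of within-participant change in walking and posture measures over the training period, with 95% confidence intervals.
2. Add one sentence, in Section 2.2 or 19.1, that this change is uncontrolled and preliminary and will not be attributed causally to the cable device.
3. Say in Section 19.2 that efficacy refers to the randomised feedback comparison, which is the one its power statement addresses.
4. Align the home self-care clause of the Primary Objective in Section 1.0 with the objectives in Section 2.1.

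The cost is wording only: no added participants, visits or measurements. The trial gives up a causal claim that it cannot support. Keeping that claim would require a comparison condition without cable training, which is a different design.

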3.0 Scientific Endpoints*

2.1 Describe the scientific endpoint(s), the main result or occurrence under study.

*NOTE: Scientific endpoints are outcomes defined before the study begins to determine whether the objectives of the study have been met and to draw conclusions from the data. Include primary and secondary endpoints. Some example endpoints are: reduction of symptoms, improvement in quality of life, or survival. Your response should **not** be a date.*

Response: The two primary outcome measures will be the motion and the muscle activation data of the lower body during walking. Motion trajectory will be used to detect the changes in the kinematics and sEMG data will present the muscle activation of the participants. Ground reaction force, center of pressure, and center of mass will be evaluated with the instrumented insole and treadmill. Before the first and after the last training, participants will be evaluated for functional gait assessment, 6-min-walk, leg strength using dynamometer, international physical activity questionnaire (short form), usability questionnaire, and Modified Ashworth test by a physical therapist. This will show the kinematic and kinetic changes of the participant after the training.

4.0 Background*

4.1 *Provide the scientific or scholarly background, rationale, and significance of the research based on the existing literature and how it will contribute to existing knowledge. Describe any gaps in current knowledge. Include relevant preliminary findings or prior research by the investigator.*

Response: Cerebral palsy is a neurological disorder that occurs around birth, impairing movement and posture which leads to critical limitations in their daily lives. About 3.6 children out of every 1000 school-aged children are diagnosed with cerebral palsy [1], and their life expectancy is significantly increased due to the advanced medical technology [2]. Past research has primarily focused on children with cerebral palsy to restore their motor function. Comparatively, attention to the adult with CP has been sparse and the evolution of the motor disorder through adulthood has not been well understood [3]. It is suggested that individuals with CP age prematurely, demonstrating early declines in physical function and mobility, presumably due to the changes in strength, flexibility, and endurance [3]. Therapeutic services have primarily been designed for children with CP without considering longer-term aging with a disability. There is a need to develop interventions that are adult-focused and can improve the motor function of individuals aging with CP.

Deterioration of locomotion skills is a major problem in persons with CP. This can lead to a sedentary lifestyle at an early age and a significant decrease in the quality of life [4]. A few studies have addressed progressive resistive strength and aerobic training in adults with CP which show significant strength improvements in their walking ability and gait parameters [5]. As an extension of these studies, we investigated the use of targeted gait training using a cable-actuated system over a treadmill that promoted strengthening during walking in children with CP [6]. This cable-actuated system provided downward force and participants had to extend their legs against the force while walking on a treadmill. This leads to a straighter walking posture, longer stride, and reduced toe-walking pattern in a supervised environment. Once the participants were taken out of the actuated cable system, they showed immediate improvement of knee extension and heel-to-toe walking. This is because participants recalibrated their movement to walk against the downward force and its effect lasted for a while after the force was removed. This after-effect of adaptation may be used in physical therapy to let the patients experience a more normal movement pattern [7]. In the proposed study, we will introduce the use of instrumented insoles to provide feedback to sustain positive after-effects in unsupervised ecological environments. Sensory feedback has been shown to improve the gait features of individuals with cerebral palsy in the past [8, 9, 10]. We will use similar methods to assist adults with CP to retain the positive motor adaptation from using the cable-actuated system on the treadmill. We will collect pressure data, foot clearance, heel-to-toe pattern from smart insoles and provide feedback to the participant on their gait pattern. We

hypothesize that once participants have experienced gait in response to resisted gait training, the feedback from the insoles will assist them to maintain the improved gait. Furthermore, we hypothesize that the use of sensory feedback with minimal supervision will lead these individuals to take an active role in their gait training. It can foster collaboration between the therapist and participant in the shared goal of improved gait quality. These are essential components of self-management, especially important for individuals with chronic conditions like cerebral palsy.

The goal of the suggested work is to retain the positive after-effects of resistive gait training for longer periods using sensory feedback until it becomes the normal gait pattern by repeated and reinforced training. For the first time, we will examine the feasibility of using sensory feedback to reinforce the adaptation from the resisted gait training. Previous robotic devices focused on the adaption itself during the training, but methods on sustaining the adaptation after the training have not been well studied, despite the significance of maintaining the adaptation. Different types of auditory feedback will be explored using the data from smart insoles to extend the carry-over effect of motor adaption during training. The knowledge of this study can be widely used in other rehabilitation devices to sustain and maximize the training effect. Secondly, this approach creates a rehabilitation platform that includes both supervised and unsupervised training which can lead to the participant taking a more active role in their care. Once participants step off the treadmill, they will use the instrumented insoles and the sensory feedback to maintain positive gait changes from the gait-resisted training. By suggesting a training method collaborating in-clinic, we envision a successful therapeutic intervention that is tailored to the needs of an adult with CP. It provides in-clinic gait resisted training to safely provide a stimulus that can alter their gait. The proposed study would also create a rich biomechanical data set over the whole gait cycle of adults with CP. Since this is an understudied population, this information would be invaluable to clinicians and researchers. This data set will help to understand neuromechanical characteristics of the gait of adults with CP for future implications in physical and pharmacological interventions, and as the long-term mission to promote healthy aging in the population with cerebral palsy by improving their functional mobility.

